8.2.1.1 Enrollment V1/V2 visit (combined with the end-of-treatment visit of parent study)

Patients will be on background asthma therapy of moderate or high-dose ICS as maintained in the parent study. Patients will also be using additional asthma controller therapies initiated during the parent study.

Please see [Appendix B](#) for a list of commonly used asthma controller medications.

8.2.1.2 Open-label treatment period

During the open-label treatment period, patients will continue the background therapy dose regimen as maintained in the parent study or as modified based on Investigator's judgment.

See [Appendix B](#) for the most commonly used asthma controller therapies.

8.2.1.3 Post-treatment period

Upon completion of the open-label treatment period (or following early discontinuation of IMP) patients will continue into the post-treatment period, with their background controller therapy dose regimen as maintained over the open-label treatment period or as modified based on Investigator's judgment (eg, taking into account the reduction of dupilumab levels over time upon completion of the treatment period).

8.2.2 Albuterol or levalbuterol reliever medication

Patients may receive salbutamol/albuterol hydrofluoroalkane pressurized metered dose inhalers (MDI) or levosalbutamol/levalbuterol hydrofluoroalkane pressurized MDI as reliever medication (as needed) during the study.

Nebulizer solutions with either albuterol/salbutamol or levalbuterol/levosalbutamol may be used as an alternative delivery method.

Study personnel should convert salbutamol/albuterol nebulizer and levosalbutamol/levalbuterol nebulizer use as shown on [Table 1](#) and [Table 2](#):

Table 1 - Conversion from Salbutamol/Albuterol Nebulizer Solution to Puffs

Salbutamol/Albuterol Nebulizer Solution – Total Daily Dose (mg)	Number of Puffs*
1.26	2
2.5	4
5	8
7.5	12
10	16

*Conversion factor: salbutamol/albuterol nebulizer solution (2.5 mg) corresponds to 4 puffs.

Example: Patient received 3 salbutamol/albuterol nebulizer treatments (2.5 mg/treatment) between 7 and 11 AM. Total daily = 7.5 mg (12 puffs).

Table 2 - Conversion from Levosalbutamol/Levalbuterol Nebulizer Solution to Puffs

Levosaltamol/Levalbuterol Nebulizer Solution – Total Daily Dose (mg)	Number of Puffs
1.25	4
2.5	8
3.75	12
5	16

Example of levosalbutamol/levalbuterol Nebulizer-to-Puff Conversion: Patient received 3 levosalbutamol/levalbuterol nebulizer treatments (1.25 mg/treatment) between 7 and 11 AM. Total daily = 3.75 mg (12 puffs).

All other reliever medications rather than albuterol/salbutamol or levalbuterol/levosalbutamol should be avoided.

8.3 BLINDING PROCEDURES

Not applicable.

8.3.1 Methods of blinding

Not applicable.

8.4 METHOD OF ASSIGNING PATIENTS TO TREATMENT GROUP

The study medication will be administered only to patients included in this study following the procedures described in the clinical study protocol. The 7-digits serialized treatment kit number will be generated centrally by sanofi clinical supply team. The IMPs are packaged in accordance with this list.

The patients will be identified by the same identification number used in the parent study. The investigational site will enter the patient tracking information for patient identification number, into the Interactive Voice Response System/Interactive Web Response System (IVRS/IWRS) during each scheduled protocol visit. The treatment allocation will be performed centrally by IVRS/IWRS. The clinical site coordinator will document the patient number and the treatment kit number in the e-CRF and in the patient's source documents, and the patient number on the IMP label prior to dispensing to the patient.

The patient will be considered to be enrolled in the study once a treatment kit number has been assigned by the IVRS/IWRS. Therefore, it is important that all inclusion/exclusion criteria are confirmed and all required procedures are completed prior to the enrollment contact to the IVRS/IWRS. Detailed IVRS/IWRS procedure will be provided in the IVRS/IWRS Site Manual.

8.5 PACKAGING AND LABELING

Note: At the time of Amendment 04, all patients have been transitioned to prefilled syringes.

The IMP dupilumab will be packaged in single-use prefilled syringes. One kit box will contain one prefilled syringe. When dupilumab administration occurs at home, enough kit boxes will be given to the patients for the period of the treatment until the next study visit.

Each packaging component will be labeled with the project and study number, a medication kit number, packaging reference number, Sponsor name, quantity or contents, dispensing instruction, caution statement, "use by" date and storage conditions. The content of the labeling is in accordance with the local regulatory specifications and requirements.

8.6 STORAGE CONDITIONS AND SHELF LIFE

The IMP should be stored at a temperature between 2°C and 8°C (36°F to 46°F) in an appropriate and locked room under the responsibility of the Investigator or other authorized persons (eg, pharmacists) in accordance with local regulations, labeling specifications, policies, and procedures.

Control of IMP storage conditions, especially control of temperature (eg, refrigerated storage) and information on in-use stability and instructions for handling the IMP should be managed according to the rules provided by the Sponsor.

8.7 RESPONSIBILITIES

The Investigator, the hospital pharmacist, or other personnel allowed to store and dispense the IMP will be responsible for ensuring that the IMP used in the clinical trial is securely maintained, as specified by the Sponsor and in accordance with applicable regulatory requirements.

All IMP will be dispensed in accordance with the Investigator's prescription and it is the Investigator's responsibility to ensure that an accurate record of IMP issued and returned is maintained.

Any quality issue noticed with the receipt or use of an IMP (deficiency in condition, appearance, pertaining documentation, labeling, expiration date, etc) should be promptly notified to the Sponsor. Some deficiencies may be recorded through a complaint procedure.

A potential defect in the quality of IMP may be subject to initiation of a recall procedure by the Sponsor. In this case, the Investigator will be responsible for promptly addressing any request made by the Sponsor, in order to recall IMP and eliminate potential hazards.

Under no circumstances will the Investigator supply IMP to a third party, allow the IMP to be used other than as directed by this clinical trial protocol, or dispose of IMP in any other manner.

8.7.1 Treatment accountability and compliance

Measures taken to ensure and document treatment compliance and IMP accountability include:

- Proper recording of treatment kit number as required on appropriate e-CRF page for accounting purposes:
- All medication treatment kits (whether empty or unused) are returned by the patient at each visit that treatment dispensing is planned.
 - The completed patient injection sheet (returned to the site at each visit), returned treatment kit boxes, and any unused prefilled syringes will be used for drug accountability purposes.
- The Investigator or designee tracks treatment accountability/compliance, either by the injection sheet or by counting the number of used treatment kits, and fills in the appropriate page of the patient treatment log.

The monitor in charge of the study then checks the data entered on the IMP administration page by comparing them with the IMP that has been retrieved and the patient treatment log form.

8.7.2 Return and/or destruction of treatments

All partially used or unused treatment kits will be retrieved by the Sponsor or destroyed at the study site. All used prefilled syringes should be kept in a sharp-container by the patients and be returned to sites for destroy. The Investigator will not destroy any unused IMP unless the Sponsor provides written authorization.

A detailed treatment log of the destroyed IMP will be established with the Investigator (or the pharmacist) and countersigned by the Investigator and the monitoring team.

8.8 CONCOMITANT MEDICATION

A concomitant medication is any treatment received by the patient concomitantly to IMP.

8.8.1 Prohibited concomitant medication

The following concomitant treatments are not permitted during the study:

- Anti-immunoglobulin E (IgE) therapy (eg, omalizumab);
- Biologic therapy;
- Systemic immunosuppressants;
- Intravenous immunoglobulin (IVIg) therapy;
- Non-selective beta-adrenergic blockers;
- Other investigational drugs;
- Live/attenuated vaccines (see [Appendix A](#)).

8.8.2 Permitted concomitant medication

The following asthma-related and other relevant concomitant treatments are permitted:

- Leukotriene antagonists/modifiers;
- Allergen immunotherapy stable dose;
- Antihistamines;
- Systemic (oral or injectable) corticosteroids:
 - Oral corticosteroids are allowed as background controller medication for the patients from EFC13691 only
 - Oral corticosteroids are allowed as treatment for asthma exacerbations and/or AEs as per Investigator's decision, for any patient;
- Ocular, intranasal or topical corticosteroids;
- Methylxanthines (eg, theophylline, aminophyllines);
- Lipooxygenase inhibitors (eg, zileuton);

- Cromones for asthma (eg, cromolyn sodium solution for nebulization, nedocromil DPI);
- Cromones for other reasons (eg, ophthalmic formulations for allergic conjunctivitis, nasal formulations for allergic rhinitis);
- Short- and long-acting anti-cholinergic drugs (ipratropium bromide and tiotropium).

8.8.3 Cytochrome P450 (CYP) precaution

The impact of dupilumab on cytochrome P450 (CYP) enzyme activity has not been studied and the effect of dupilumab on levels of IL-4 and IL-13 has not been fully characterized.

However, IL-4 was reported to up-regulate CYP2E1, 2B6, 3A4 mRNA expression or down-regulate CYP1A2 mRNA (12, 13). Human peripheral blood mononuclear cells (PBMC) incubated with various Th2 cytokines showed that IL-4 and IL-13 increased mRNA expression of CYP2B6 and CYP3A4 (14). Since the clinical significance of the limited in vitro findings for IL-4 and IL-13 involvement in CYP regulation and the impact of dupilumab on CYP enzymes is not fully understood, during the study treatment and at least up to the end of follow-up, caution should be used for drugs which are metabolized via these CYP isoforms and which have a narrow therapeutic index. Close clinical observation and/or laboratory monitoring as applicable are required when the investigational product is started or stopped in order to enable early detection of toxic manifestations or lack of activity/efficacy of these drugs, followed by dose adjustment or their withdrawal if needed. Some examples of CYP450 substrates with narrow therapeutic index are provided in [Appendix C](#).

9 ASSESSMENT OF INVESTIGATIONAL MEDICINAL PRODUCT

9.1 PRIMARY ENDPOINT

The primary endpoint of this study is the number (n) and percentage (%) of patients experiencing any treatment-emergent adverse events (TEAE).

Adverse events, serious adverse events (SAEs), adverse events of special interest (AESI), AEs leading to IMP discontinuation and death will be collected from the date of the signed informed consent form (ICF) for participation in LTS12551 (planned at the Combined V1/V2 Visit). The study specific and general safety criteria are detailed in [Section 10.4.1](#). To assure the continuing safety of patients in this study, an Independent DMC will be responsible for reviewing the safety data on a periodic basis throughout the course of the study as outlined in [Section 6.2](#).

Adverse events, AESIs, SAEs, AEs leading to IMP discontinuation and deaths will be reported as described in [Section 10.4.1](#) and analyzed as in [Section 11.4.3](#).

Safety Observations

- The Investigator should take all appropriate measures to ensure the safety of the patients. Notably, he/she should follow-up the outcome of SAEs/AESIs until clinical recovery is complete and laboratory results have returned to normal, or until progression has been stabilized, or death. In all cases, this may imply that observations will continue beyond the last planned visit per protocol, and that additional investigations may be requested by the Sponsor.
- When treatment is prematurely discontinued, the patient's observations will continue until the end of the study as defined by the protocol for that patient.
- In the case of any SAE/AESI requiring immediate notification, being brought to the attention of the Investigator at any time after the end of the study for the patient, and considered by him/her to be caused by the investigational product with a reasonable possibility, this should be reported to the Sponsor.

9.2 SECONDARY ENDPOINTS

9.2.1 Safety and tolerability

The following parameters will be analyzed (see also [Section 11.4.3.1.4](#) for analysis):

- Vital signs.
- Physical examination.
- Electrocardiogram (ECG) variables.
- Clinical laboratory tests.

9.2.1.1 Vital signs

Vital signs, including blood pressure (mmHg), heart rate (beats per minute), respiratory rate (breaths per minute), body temperature (degrees Celsius), and body weight (kg) will be measured at every scheduled treatment visit (see flow charts [Section 1.2](#) and [Section 1.3](#)). Height (cm) will only be measured at enrollment. Vital signs will be measured in the sitting position using the same arm at each visit, and will be measured prior to receiving investigational product at the study visits.

9.2.1.2 Physical examination

Physical examinations will include an assessment of general appearance, skin, eyes, ear/nose/throat, heart, chest, abdomen, reflexes, lymph nodes, spine, and extremities. All deviations from normal will be recorded, including those attributable to the patient's disease. Physical examinations will be performed as per the schedule of assessments (see flow charts [Section 1.2](#) and [Section 1.3](#)).

9.2.1.3 Electrocardiogram (ECG) variables

A 12-lead ECG will be performed as per the schedule of assessments (see flow charts [Section 1.2](#) and [Section 1.3](#)). A minimum of 3 complexes in an appropriate lead (lead II) will be averaged to determine the PR-interval, QT/QTc-interval, and QRS-complex (and heart rate will also be measured) for each ECG.

The Investigator should review the ECG and document his interpretation, signed and dated on the ECG print out. The original trace is kept as source data. Electrocardiogram tracings are also read manually by independent, certified and "centralized" cardiologists, who determine ECG parameters and who in addition alert the Investigator and the Sponsor of any clinically significant findings or changes. These manually read tracings are the ECG tracing of record for this clinical trial. A specific written manual regarding the procedures related to the centralized ECG reading are provided to each Investigator. Refer to the ECG manual for further details.

Notes: Any abnormal ECG parameter should be immediately rechecked for confirmation before making a decision of permanent discontinuation of treatment with dupilumab for the concerned patient.

9.2.1.4 Clinical laboratory tests

The clinical laboratory tests will be conducted by an accredited central laboratory with national and regional clinical licenses, as required for diagnostic testing, and must provide evidence of participation in proficiency testing, as appropriate. After reviewing the laboratory report and evaluating any results that are outside the normal range, the Investigator must sign and date the laboratory report. Abnormal laboratory values that are considered to be clinically significant by the Investigator must be repeated as soon as possible after receiving the laboratory report, to rule out laboratory error. Persistent abnormal laboratory values should be repeated until they return to normal or until an etiology of the persistent abnormality is determined.

The following laboratory tests will be performed (as per the schedule of assessments, see flow charts in [Section 1.2](#) and [Section 1.3](#)). Patients will be informed of fasting requirements for hematology and serum chemistry assessments.

- Hematology: Blood count (erythrocytes, hemoglobin, hematocrit, leukocytes), differential blood count (neutrophils, lymphocytes, monocytes, eosinophils, and basophils) and platelets.
- Serum chemistry: Total bilirubin (in case of values above the normal range, differentiation in conjugated and non-conjugated bilirubin), alanine aminotransferase (ALT), aspartate aminotransferase (AST), alkaline phosphatase (ALP), total protein, albumin, total cholesterol, creatine phosphokinase (CPK), glucose, creatinine, blood urea nitrogen (BUN), uric acid, bicarbonate, and electrolytes (sodium, potassium, and chloride).
- Urine analysis: pH, glucose, ketones, leukocyte esterase blood, protein, nitrate, urobilinogen, and bilirubin (by dipstick). If any parameter on the dipstick is abnormal, a urine sample should be sent to the central laboratory for testing. If positive for proteins, microscopic analysis is performed by central laboratory.
- Serum immunoglobulin, including IgE, are no longer to be assayed due to Amendment 04.
- Clinical laboratory testing: hepatitis screen (HBsAg, HBcAb-IgM), HCVAb, HIV screen (anti-HIV-1 and HIV-2 antibodies), and anti-nuclear antibody (ANA). Anti-ds DNA antibody will be tested if ANA is positive ($\geq 1:160$ titer). Japanese patients who have rolled over from DRI12544 study should be retested for hepatitis B (HBsAg, HBsAb, and HBcAb), after Visit 1, at any time during the LTS12551 study, via the earliest scheduled study visit, after IRB approval for Local Amendment 03 (Japan).
- Hepatitis B viral load testing: For patients in Japan (or other countries/regions if there is local regulatory requirement) who were HBsAg negative and HBsAb positive at screening during the parent study, or at the additional test due to Local Amendment 03 (Japan).

Decision trees for the management of certain laboratory abnormalities by Sanofi are provided in [Appendix D](#).

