10.3.3 List of criteria for permanent treatment discontinuation

The patients may withdraw from treatment with the IMP if they decide to do so, at any time and irrespective of the reason, or this may be the Investigator's decision. All efforts should be made to document the reasons for treatment discontinuation and this should be documented in the e-CRF.

Any abnormal laboratory value or ECG parameter should be immediately rechecked for confirmation (within 24 hours) before making a decision of permanent discontinuation of the IMP for the concerned patient. Threshold values for the discontinuation of IMP are defined in collaboration with Global Pharmacovigilance and Epidemiology (see [Appendix D](#)).

The following criteria will lead to permanent treatment discontinuation:

- At their own request or at the request of their legally authorized representative (legally authorized representative means an individual or judicial or other body authorized under applicable law to consent on behalf of a prospective patient to the patient's participation in the procedure(s) involved in the research).
- If, in the Investigator's opinion, continuation in the study would be detrimental to the patient's well-being (see also safety [Section 10.6](#)).
- At the specific request of the Sponsor.
- In the event of a protocol deviation, at the discretion of the Investigator or the Sponsor.
- Pregnancy (Note: dupilumab should be stopped but patient should be followed up until delivery).
- Anaphylactic reactions or systemic allergic reactions that are related to IMP and require treatment.
- Diagnosis of a malignancy during study, excluding carcinoma in situ of the cervix, or squamous or basal cell carcinoma of the skin.
- Any opportunistic infection, such as tuberculosis (TB) or other infections whose nature or course may suggest an immunocompromised status (See [Appendix I](#)).
- Serum ALT >3 Upper Limit of Normal (ULN) concurrent with Total Bilirubin >2 ULN (see [Appendix D](#)).
- Serum ALT >5 ULN if baseline ALT < 2 ULN or ALT >8 ULN if baseline ALT >2 ULN ([Appendix D](#)).

Note: Any abnormal laboratory value or ECG parameter will be immediately rechecked for confirmation before making a decision of permanent discontinuation of the IMP for the concerned patient.

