2.5.4 Windows for time points

For the safety assessment, the reference date for the derivation of relative days of events or findings will be the date of first IMP dose injection in LTS12551 study. Selected safety variables will be summarized by the analysis window defined in Table 5 for the by-visit descriptive analysis. For all laboratory/vital sign/ECG variables, the summary statistics over visits for either measurements or mean change from baseline, and the plot of mean change from baseline over visits should use the centralized data only (if applicable), and should include the measurements obtained at either scheduled or unscheduled visits. For PCSA analyses, the measurements of laboratory/vital sign/ECG variables obtained at either scheduled visits or unscheduled visits should be used; and, both the centralized and local test results should be used (if applicable), as long as their available dates/time are different from each other's. All available safety measurements (from either scheduled or unscheduled visit) will be assigned to the appropriate visit window. In the event of multiple measurements of the same test in the same window, the one closest to the targeted visit date will be used for the by-visit summary. If they are at the same distance to the target day, the latest one will be used.

The pre-dose measurements at Week 0 of LTS12551 are defined as follows: for patients enrolled from DRI12544, the measurements at Week 0 are obtained from the EOS visit of DRI12544 if available, regardless whether the EOS visit in DRI12544 was combined with Visit 1/Visit 2 in LTS12551; otherwise, Week 0 value will be the last available measurement prior to the first IMP dose in LTS12551 study. For patients enrolled from EFC13579, EFC13691 and PDY14192, the measurements at Week 0 are obtained from the EOT visit of parent studies if available; otherwise, Week 0 value will be the last available measurement prior to the first IMP dose in LTS12551 study.

		Target	Vital	Signs	EC	CG	Physical Ex Urine A	xamination, Analysis	Hematolo Cher	gy, Serum nistry
VISIL	VVEEK	day	Minimum days	Maximum days	Minimum days	Maximum days	Minimum days	Maximum days	Minimum days	Maximum days
1 & 2	0	Derived		Up to 1st IMP dose date/time						
3	2	15	After 1st IMP dose date/time	21						
4	4	29	22	35					After 1st IMP dose date/time	56
5	6	43	36	49						
6	8	57	50	63						
7	10	71	64	77						
8	12	85	78	98			After 1st IMP dose date/time	126	57	126
9	16	113	99	126						

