10	20	141	127	154						
11	24	169	155	210	After 1st IMP dose date/time	252	127	252	127	252
12	36	253	211	294						
13	48	337	295	378	253	504	253	420	253	420
14	60	421	379	462						
15	72	505	463	546			421	546	421	588
16	84	589	547	630			547	630		
17 (EOT)	96	673	631	d*	505	d*	631	d*	589	d*
18 (EOS)	108	757	d*+1		d*+1		d*+1		d*+1	

Table 5 - Time window for safety variables

*Note: d= max (last IMP dose +14 days, EOT date)

Statistical Analysis Plan SAR231893-LTS12551 - dupilumab

20-Jul-2017 Version number: 3

Vicit	Wook	Target day	Pregnar	ncy Test	Serum Immunoglobulin		
VISIL	Week	Taiget day	Minimum days	Maximum days	Minimum days	Maximum days	
1 & 2	0	Derived		Up to 1st IMP dose date/time		Up to 1st IMP dose date/time	
3	2	15					
4	4	29	After 1st IMP dose date/time	35			
5	6	43	36	49			
6	8	57	50	63			
7	10	71	64	77			
8	12	85	78	98			
9	16	113	99	126			
10	20	141	127	154			
11	24	169	155	210	After 1st IMP dose date/time	252	
12	36	253	211	294			
13	48	337	295	378	253	462	
14	60	421	379	462			
15	72	505	463	546			
16	84	589	547	630	463	630	
17 (EOT)	96	673	631	d*	631		
18 (EOS)	108	757	d*+1				

*Note: d= max (last IMP dose +14 days, EOT date)

For the efficacy assessment, the reference date for the derivation of relative days of events or findings will be the day of the first IMP injection in LTS12551 study. And for the endpoints not measured daily, all available values of scheduled measurements will be assigned to the appropriate visit window according to Table 6. In the event of multiple measurements of the same test in the same window, the one closest to the targeted visit date will be used for the by-visit summary. If they are at the same distance to the target day, the latest one will be used. The pre-dose measurements at Week 0 of LTS12551 are defined in the same way as in the paragraph prior to Table 5.

Vioit	Wook	Spirometry		ACQ-5, AQLQ		
		Target day	Minimum days Maximum days		Minimum days	Maximum days
1&2	0	Derived		1 st IMP dose date/time (Day 1)		1 st IMP dose date/time (Day 1)
3	2	15	2	21		
4	4	29	22	42		
5	6	43				
6	8	57	43	70		
7	10	71				
8	12	85	71	126		
9	16	113				
10	20	141				
11	24	169	127	252	2	252
12	36	253				
13	48	337	253	420	253	
14	60	421				
15	72	505	421	546		
16	84	589	547	630		
17 (EOT)	96	673	631	d*		
18 (EOS)	108	757	d*+1			

Table 6 - Time window for efficacy variables

*Note: d= max (last dose +14 days, EOT date)

Visit Week Target day		EQ-5D, R	esource Utilization	Prescribed	Prescribed OCS dose		

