2.5.5 Unscheduled visits

Unscheduled visit measurements of laboratory data, vital signs, and ECG will be included in the by-visit summaries and figures, as well as the computation of baseline, worst values, and PCSAs.

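### By-visit laboratory tables, and a few ECG values, can show an abnormality-triggered central repeat in place of the scheduled result, pulling them slightly toward normal

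*Protocol*

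**What the plan says.** **What triggers a repeat.** Protocol section 9.2.1.4 states that "Abnormal laboratory values that are considered to be clinically significant by the Investigator must be repeated as soon as possible" once the report has been received, to exclude laboratory error. It adds that "Persistent abnormal laboratory values should be repeated until they return to normal or until an etiology of the persistent abnormality is determined". For ECGs, Protocol section 9.2.1.3 says: "Any abnormal ECG parameter should be immediately rechecked for confirmation before making a decision of permanent discontinuation". Section 10.3.3 applies the same recheck to laboratory and ECG values, within 24 hours, again ahead of a decision to stop treatment permanently.

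**What the SAP tabulates.** SAP section 2.5.5 says: "Unscheduled visit measurements of laboratory data, vital signs, and ECG will be included in the by-visit summaries and figures". Sections 2.4.5.3 and 2.4.5.5 restrict laboratory and ECG by-visit summaries and plots to central data, from scheduled or unscheduled visits. Section 2.5.4 assigns all these values to the safety windows. Where a window holds several values it keeps the one nearest the target day, and for ties: "If they are at the same distance to the target day, the latest one will be used". Nothing gives the scheduled value priority.

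**What the SAP does elsewhere.** For efficacy endpoints not measured daily, section 2.5.4 says that "all available values of scheduled measurements will be assigned to the appropriate visit window". The pharmacokinetic and pharmacodynamic windows are likewise limited to scheduled measurements.

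**The concern.** No passage calls for a repeat of a normal result. Whether a second value exists therefore depends on the first, and the window rule can then discard the first. Regression to the mean, recovery and corrected laboratory errors all make the second value, on average, closer to normal. A by-visit table built this way loses some of its abnormal scheduled values and none of its normal ones.

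The by-visit tables and mean-change plots show when an abnormality appears and how the distribution moves over time. They report minimum, maximum and SD at each visit, and those are most sensitive to a few removed values. A visit row may also fail to show a value that was counted in the PCSA table.

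Eosinophil count illustrates the inconsistency. It is a haematology variable under the safety windows, where unscheduled values are allowed, and a pharmacodynamic variable, for which section 2.5.4 refers to scheduled measurements only. Table 7 has no eosinophil column to settle which rule applies.

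**Working it through.** The documents give no figure on this point, so there is none to reproduce. The check applies the window rule as written.

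**Inputs from the documents**
- Visit windows: ±3 days in the first 12 weeks, ±7 days afterwards (Protocol sections 1.2 and 1.3, footnote a). Post-baseline laboratory draws at Weeks 4 and 12 fall under ±3 days. Later draws, and all post-baseline ECGs (the first is at Week 24), fall under ±7 days.
- Selection rule: nearest to target, latest if tied (SAP section 2.5.4).

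**Assumptions**
- Visit dates are uniform over the allowed days.
- Values are standard normal, and the top 2.5% trigger one central repeat.
- The correlation r between scheduled and repeat value is 0.5 to 0.9, with no true change between them.

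The documents give no repeat rates, lags or correlations.

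**Step 1: when the repeat wins.** Let s be the scheduled visit's offset from the target day and L the lag to the repeat. The repeat is tabulated when |s + L| ≤ |s|. For L = 0 this always holds, because the values tie and the later one is used. For L > 0 it reduces to s ≤ −L/2, so the visit must have been early by at least half the lag.

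| Lag | ±7 days (15 possible days) | ±3 days (7 possible days) |
|---|---|---|
| 0 | 15/15 = 100% | 7/7 = 100% |
| 1 day | 7/15 = 47% | 3/7 = 43% |
| 3 days | 6/15 = 40% | 2/7 = 29% |
| 7 days | 4/15 = 27% | 0/7 = 0% |

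One exception arises if Table 5 is read literally. Its end-of-study target is Day 757 for everyone, while a 48-week patient's end-of-study visit is near Day 421. Any later central repeat in that window is then nearer the target and replaces the visit value.

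**Step 2: share of tabulated values beyond the trigger.** Let p be the replaced share and q the chance that the repeat is also beyond the trigger. The tabulated share is 2.5% × [1 − p(1 − q)]. The bivariate normal gives q = 0.185 at r = 0.5 and q = 0.593 at r = 0.9. For lags of 1 to 7 days in ±7-day windows:
- Largest effect (1 day, r = 0.5): 2.5% × [1 − 0.467 × 0.815] = 1.55%.
- Smallest effect (7 days, r = 0.9): 2.5% × [1 − 0.267 × 0.407] = 2.23%.

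**Step 3: shift of the mean.** If every triggered value were replaced, the mean would move by φ(1.96) × (1 − r) = 0.0584 × (1 − r). That is 0.029 SD at r = 0.5 and 0.006 SD at r = 0.9. Multiplying by the replaced share gives 0.467 × 0.029 = 0.014 SD at most and 0.267 × 0.006 = 0.002 SD at least. In ±3-day windows the effect is smaller, and zero at a 7-day lag.

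**Step 4: effect on spread.** A separate simulation used a trigger of +2 SD, r = 0.7, ±7 days and a 1-day lag. The SD fell from 1.000 to 0.987, and the share above 2 SD from 2.28% to 1.56%.

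**The case against.** A prespecified closest-to-target rule is a common and mechanical convention, and the safety analysis is descriptive with no systematic testing. The extremes most affected are reported elsewhere. PCSA incidence uses every evaluation, including repeats (SAP section 2.4.5). The worst on-treatment nadir or peak is summarised separately. Patients with a post-baseline PCSA have their whole profile listed (section 2.4.5.3). Peak eosinophil counts have their own table (section 2.4.6.2). The first repeat is meant to exclude laboratory error, so some replacements are corrections. A worsening abnormality would give a more abnormal repeat, so the pull toward normal holds only on average. All of this stands, and it limits the point to low severity.

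Four stronger inferences are tempting and are not supported:

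- **Every abnormal ECG is rechecked and overwritten.** Protocol sections 9.2.1.3 and 10.3.3 tie the recheck to a permanent-discontinuation decision and allow 24 hours. Only centrally read tracings enter the by-visit tables. Few ECG values are involved.
- **Most abnormal laboratory values disappear.** A fall from 2.5% to about 0.5–1.5% requires every repeat to replace its scheduled value, as with same-day repeats. Laboratory repeats follow receipt of the report, so lags of a day or more are the more realistic case. The Investigator must also judge the value clinically significant, so the 2.5% trigger is itself only illustrative.
- **Vital signs are distorted in the same way.** The window rule covers them, but section 9.2.1.1 has no abnormality-triggered repeat for them.
- **The primary safety result is biased.** The primary endpoint is the number and percentage of patients with any TEAE, which this rule does not touch.

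What the objection does not answer is that the tabulated value depends on an outcome-triggered repeat, and that the same SAP avoids this for efficacy and PK/PD.

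**Conclusion.** The point holds as a low-severity flaw in record selection. SAP sections 2.5.4 and 2.5.5 allow a central repeat, taken because a result was abnormal, to displace the scheduled value in by-visit laboratory summaries and plots, and in a small number of ECG values. On average this pulls them toward normal.

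For lags of 1 to 7 days in ±7-day visit windows, the mean moves by about 0.002 to 0.014 SD and the share beyond the trigger falls from 2.5% to 1.55–2.23%. By-visit minimum, maximum and SD are affected most. These sizes rest on uniform visit dates, a top-2.5% trigger, one central repeat and correlations of 0.5 to 0.9, none of which the documents supply. The mechanism and its average direction do not depend on those values.

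The primary TEAE endpoint, PCSA incidence, worst on-treatment values, PCSA listings and the eosinophil peak table are unaffected. A reader should not infer that the trial's safety conclusions are at risk.

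**What to change.** In SAP sections 2.5.4 and 2.5.5, state that laboratory and ECG by-visit summaries and plots use the scheduled-visit central result whenever one exists. An unscheduled central value is used only if the scheduled one is missing or flagged invalid by the laboratory. Keep all scheduled, unscheduled and repeat values for PCSA, worst-value and listing outputs, as now.

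This reduces replacement to zero and brings the safety windows into line with the SAP's efficacy and PK/PD convention. The cost is about one sentence and a change to the record-selection step in programming. The downside is that an erroneous scheduled value that was not flagged invalid stays in the by-visit summary. Results that the laboratory does flag invalid are already excluded under SAP section 2.5.3.
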